#### Responsibilities of sponsor/marketing authorization holder (MAH)

Independently of the regulatory obligations of investigator, the sponsor/MAH must report the pharmacovigilance data to the appropriate authorities in accordance with the Good Vigilance Practice and local regulations.

Cases are closed when an adverse event has recovered or patient's condition was stabilized and the report is deemed sufficiently detailed for adequate medical analysis of the case.

#### Data Management

- Data collection in this study is carried out using documentation forms. Centralized data entry will be performed by the responsible professional subcontractor for statistical analyses after receiving the documentation forms. The statistical analysis of the data and the creation of the final statistical report on the study will also be carried out by a responsible professional subcontractor for statistical analyses.
- Discrepancies will be resolved by mutual agreement between both parties (Servier and professional subcontractor for statistical analysis).

#### **Biometrics**

- Due to the non-interventional nature of this study, statistical analysis will be conducted in a descriptive and searchable form. All indicators will be analyzed using descriptive statistics methods. For each indicator, the number of patients, the average value, the standard error, the minimum and maximum values, or the proportion of each category will be specified. All composite indicators will be
- listed and presented in visual form as graphs and frequency distribution tables / indicator tables.
- Absolute and percentage frequencies will be calculated for categorical variables. Only patients for whom data on the corresponding variables will be available will be included in the relative frequency calculations.
- All reports of adverse drug reactions, adverse events, and special situations will be coded using MedDRA, and the results will be listed and classified according to classes for organ and organ systems (system-Organ-Class; SOC) by the statisticial agency during preparation of final report.

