## Study variables

## **Primary variables:**

• Mean change from baseline (BL) in total HAMD-17 score assessed at week 8 of the observational period.

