# Methods and documentation

# Study design and methodology

This is a multi-centre, observational, non-interventional study, which will prospectively collect clinical and socio-demographic data from patients with depression occurred after COVID 19 in real clinical settings during 8 weeks of treatment.

At Visit 0 (V0), investigating psychiatrist or neurologist will evaluate patient's eligibility for the study according to inclusion/non-inclusion criteria. Only patients who comply with all inclusion/ non inclusion creteria will be invited to participate in this observational study. Recommendation to start treatment with agomelatine to manage depressive episode is to be done by investigating psychiatrist/ neurologist before and independently from the decision to invite a patient to participate in the study. Agomelatine should be administered to patients in accordance to the instruction for medical use approved in the Russian Federation (RF).

20 clinics and 20 of psychiatrists and neurologists across the country will participate in the study and it is estimated that each investigating physician will enroll at least 5 of patients.

Once a patient will provide his/her consent to participate in the study, investigating physician will record information from appointments for the evaluation of treatment in a routine clinical practice. The frequency of the appointments reflects a routine clinical practice of management of outpatients with depressive disorders in the RF.

Main millestones:

Local Ethic Committee approval – 1q22 First patient included – March 2022 Last patient included – July 2022 End of treatment period – September 2022 Clinical statistic subdevelopment – August 2022 Data based lock – October 2022 Clinical statistic subdevelopment report – November-December 2022 End of clinical study – February 2023

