# Study plan and procedures

A patient with depression occurred within 3 month period after onset of confirmed COVID 19 infection who has already been recommended to initiate antidepressive treatment with agomelatine will be asked to provide a consent to participate in the study and in case of consent is positive the patient will be invited for 3 more visits starting from the date of the inclusion in the study according to clinical practice. Therefore clinical parameters needed for describing effectiveness and tolerability of agomelatine treatment will be prospectively collected at each of these visits.

Antidepressive treatment of enrolled outpatients can be modified by investigating psychiatrist or neurologist at any time of the observation if required.

Following visits are planned:

- 1. Inclusion Visit 0 (V0) inclusion in the study
- 2. Follow up Visits 1-2 (V1-V2) visits at week 2 and week 4 after V0.
- 3. Final Visit 3 (V3) visit at week 8 after V0.

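### The standard error planned for the mean week-8 HAMD-17 change makes no allowance for patients being grouped under 20 physicians, so it is likely too small if change is correlated within physician.

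*Combined protocol and SAP*

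**What the plan says.** The primary variable is "Mean change from baseline (BL) in total HAMD-17 score assessed at week 8 of the observational period". The Biometrics section states that "All indicators will be analyzed using descriptive statistics methods" and lists, for numeric indicators, "the number of patients, the average value, the standard error, the minimum and maximum values". Categorical indicators such as response and remission get counts and percentages. No formula is given for the standard error, and no confidence interval is planned.

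On structure, Study design and methodology says that "20 clinics and 20 of psychiatrists and neurologists across the country will participate in the study" and that "it is estimated that each investigating physician will enroll at least 5 of patients". After consent, the "investigating physician will record information from appointments for the evaluation of treatment in a routine clinical practice". Study plan and procedures adds: "Antidepressive treatment of enrolled outpatients can be modified by investigating psychiatrist or neurologist at any time of the observation if required".

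Centre effects, physician effects, clustering, an intraclass correlation (ICC), a mixed model and a robust variance are mentioned nowhere. The only inferential model, the one-sample t-test behind the sample size in the Statistical analysis section, assumes independent patients.

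**The concern.** One physician enrols, manages and follows each group of patients. Specialty (psychiatry or neurology), local practice, case mix and drift in rating over the 8 weeks could all make the change in HAMD-17 more alike within a physician than between physicians. Each further patient of the same physician then adds less information than a patient of a new one, and the usual standard error, SD divided by the square root of n, is too small.

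This matters because the study has a single arm and is descriptive. Its main product is the estimated change and the error bar on it. A reader who turns the published standard error into an interval would take the change to be known more precisely than it is.

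**Working it through.** **1. The plan's own figure.** A one-sample t-test with a difference of 3.0 points, SD 3.8 and one-sided alpha 0.005 has power 0.90991 at n = 28 (noncentral t), as the plan states. Dropout of 30% gives 28 / 0.70 = 40, also as stated. The calculation has no cluster term.

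**2. Inputs.** From the document: 20 physicians, at least 5 patients each (20 × 5 = 100), 30% dropout (70 evaluable, 70 / 20 = 3.5 per physician), SD 3.8. Assumed: an ICC of the change between 0 and 0.20, because the document gives none.

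**3. Formulas.** Design effect DE = 1 + (m − 1) × ICC; multiplier of the standard error = √DE; effective n = n / DE. The independence standard error is 3.8 / √100 = 0.380, or 3.8 / √70 = 0.454. For example, with m = 5 and ICC 0.10, DE = 1 + 4 × 0.10 = 1.40, √1.40 = 1.18, and the standard error is 0.450.

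| Assumed ICC | m = 5: DE | SE multiplier | SE | Effective n of 100 | m = 3.5: DE | SE multiplier | SE | Effective n of 70 |
|---|---|---|---|---|---|---|---|---|
| 0 | 1.00 | 1.00 | 0.380 | 100 | 1.000 | 1.00 | 0.454 | 70 |
| 0.01 | 1.04 | 1.02 | 0.388 | 96 | 1.025 | 1.01 | 0.460 | 68 |
| 0.05 | 1.20 | 1.10 | 0.416 | 83 | 1.125 | 1.06 | 0.482 | 62 |
| 0.10 | 1.40 | 1.18 | 0.450 | 71 | 1.250 | 1.12 | 0.508 | 56 |
| 0.20 | 1.80 | 1.34 | 0.510 | 56 | 1.500 | 1.22 | 0.556 | 47 |

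The standard errors in points are illustrative. The SD of 3.8 equals the spread of the HAMD-17 score of 15.3 in the cited study and is not shown to be an SD of change. The multipliers do not depend on it.

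**4. Cluster size.** Five is a minimum, and recruitment will be uneven. With mean size 5 and a coefficient of variation of 0.5 (assumed), DE at ICC 0.10 is 1 + ((1 + 0.25) × 5 − 1) × 0.10 = 1.525, and the multiplier is 1.23 instead of 1.18.

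**5. What a reader's interval would cover.** The plan has no confidence interval. If a reader built a nominal 95% interval from the independence standard error, its coverage would be about 2Φ(1.96 / √DE) − 1. With m = 5 that is 93%, 90% and 86% at ICC 0.05, 0.10 and 0.20.

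**6. Sample size.** At ICC 0.20 and m = 5, the 28 patients become 28 × 1.8 = 50.4, so 51, and 51 / 0.70 gives 73 enrolled. That is below the planned 100. With 70 completers and ICC 0.20, power for 3.0 points is still about 99.6%.

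**The case against.** The other side has several good points.

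- **The correlation is not documented.** At ICC 0 nothing changes, and at 0.01 the standard error with 5 per physician moves by 2%. This stands, and the conclusion must be conditional.
- **Rater style is a weak mechanism for this endpoint.** If one physician rates both baseline and week 8, a constantly lenient or severe style largely cancels in the change. This stands. What remains is specialty, local practice, case mix and drift. The document also does not name the HAMD-17 rater; that it is the investigating physician is a natural reading only.
- **The independence formula is inferred.** Biometrics gives none. With no cluster term anywhere and a one-sample t-test as the only model, the ordinary formula is still the natural reading.
- **Response and remission have no planned standard error.** This stands. For them the point applies only if an interval is added.
- **The effect is small beside the expected change.** With 100 patients the largest shift above is 0.510 − 0.380 = 0.13 points, while the cited study's mean fell by 15.3 − 4.7 = 10.6. This stands as a limit on importance. It does not justify a misstated error bar when the error bar is part of the result.

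A reader might go further and infer that the study is too small or that the estimated change is biased. Neither follows: 100 exceeds the clustered requirement of 73, and leaving out the adjustment does not by itself bias the mean.

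**Conclusion.** The concern holds in conditional form. The plan reports a standard error with no allowance for patients nested in 20 physicians, and that standard error is likely too small if change in HAMD-17 is positively correlated within physician. Over an assumed ICC of 0 to 0.20 the understatement is a factor of 1.00 to 1.34 with 5 patients per physician and 1.00 to 1.22 with 3.5 evaluable. Larger or uneven groups would raise it.

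The document does not support the flat statement that the error bars are too narrow, because that needs a positive correlation which it does not give. This is a minor improvement to how precision is reported. It does not threaten the study's main finding.

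**What to change.** Add to Biometrics: the standard error and a 95% confidence interval of the mean week-8 HAMD-17 change will be computed with physician or site as the cluster, by a cluster-robust variance with a small-sample correction for 20 clusters or by a random intercept. Use the same approach for any interval given for response and remission. The robust variance keeps the plan's simple mean; a random intercept reweights physicians when their groups differ in size.

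State that a physician or site code is kept in the analysis dataset. The lists of collected data do not include one, and the confidentiality section mentions only a unique patient number.

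No extra patients or visits are needed. Intervals become slightly wider even if the correlation is zero: with SD 3.8 and 100 patients, the 95% half-width goes from 0.754 (t, 99 df) to 0.795 (t, 19 df) at ICC 0, and to 0.941 at ICC 0.10. Any reported ICC will be imprecise. At a true value of 0.10 its large-sample standard error, √[2(1 − ICC)² DE² / (m(m − 1)(k − 1))] with k = 20, is about 0.09 for m = 5 and 0.12 for m = 3.5. A random-intercept variance may therefore be estimated at zero, and the ICC should be presented as descriptive only.

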## **Publications and communication**

• The sponsor is responsible for communicating and publishing research data. No part of the results of this study or other data may be published, presented or distributed without the express written permission of Sponsor. Participants in the study fully transfer to the Sponsor the authority for the first presentation, communication and publication of the results on behalf of all employees. No other communication or publication is permitted before this first publication. Any subsequent communication or publication must first be reviewed and approved by the Sponsor and should refer to the research and the first publication.

# Ethic aspects

- The study will be conducted in accordance with the principles of the Helsinki Declaration, according to the version revised in Brazil in 2013.
- The Protocol must be reviewed and approved by an independent ethics Committee after being submitted by the coordinator or sponsor in accordance with local regulatory requirements, especially with regard to data protection.

#### Confidentiality of patient data

• Researchers are required to maintain the confidentiality of information about patients included in this study. Confidential data should contain enough information to contact the patient in case of an emergency, or if further monitoring is required.

To protect data privacy and keep patients anonymous, their identity will be encoded in the research documentation. Patients can be identified using a unique number that will be recorded and the CRF. In order to reveal the patient's identity, all researchers will have a confidential list of patient identification containing the names and phone numbers. Thus, only the researcher will be able to decode the patient's identity.

# Appendix 1. THE HAMILTON RATING SCALE FOR DEPRESSION (HAMD-17)

#### Instructions.

1

For assessment please choose one answer that best characterizes the patient's condition.

For item 7 (work and activities) the researcher can obtain information from relatives or medical personnel.

Item 16 (weight loss) requires an answer only by one of the proposed points 16A and 16B according to the "yes or no". The assessment of body weight changes is more preferable during therapy (16B). The assessment of weight change on anamnestic information (16A) is used only as initial, before starting therapy.

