#### A. When rating by history:

- 0- No weight loss
- 1- Probably weight loss associated with present illness
- 16B2- Definite (according to patient) weight loss
  - 3- Not assessed

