#### B. If loss of weight is observed each week and is actual now

- 0- Less than 0.5 kg per week
- 1- More than 0.5 kg per week
- 2- more than 1 kg per week
- 3- Not assessed

#### 17

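### HAMD-17 item 16 is rated on weight-loss history before therapy and on current rate of loss afterwards, which can put up to 2 points of apparent improvement per patient into the primary change score

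*Combined protocol and SAP*

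**What the plan says.** All references are to the combined protocol and SAP.

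- **Which version is used when.** In Appendix 1, Instructions, item 16 "requires an answer only by one of the proposed points 16A and 16B". On the history version: "The assessment of weight change on anamnestic information (16A) is used only as initial, before starting therapy". The same paragraph calls 16B preferable during therapy.
- **What 16A measures.** In Appendix 1, item 16 part A, the top substantive score of 2 is "Definite (according to patient) weight loss". It carries no rate and no look-back period.
- **What 16B measures.** Part B is headed "If loss of weight is observed each week and is actual now". Its zero is "Less than 0.5 kg per week", and 2 means more than 1 kg per week.
- **Code 3.** Both versions print a 3 for an item that was not assessed. No rule keeps that 3 out of the total.
- **Where the total is used.** The primary variable is "Mean change from baseline (BL) in total HAMD-17 score assessed at week 8 of the observational period". Under Secondary variables, response is a fall in the total of at least 50% and remission is a week-8 total below 7.
- **When it is rated.** Table 1 lists the HAMD-17 at V0 and at weeks 2, 4 and 8.

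Neither Statistical analysis nor Biometrics describes an analysis without item 16.

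**The concern.** A change score assumes that the same quantity is measured at both ends. For item 16 the instructions measure weight already lost at the start and weight being lost now at the end. A patient who lost weight before V0 and has been stable since can score 2 and then 0 without any change in condition.

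This study has no control arm in which the same artefact would appear and cancel. The reported mean change is the result, so a fall produced by the rating form is read as effectiveness. Response is exposed too, because an inflated baseline makes a 50% fall easier to reach.

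**Working it through.** **1. The plan's own figure.** Statistical analysis sizes the study on a one-sample t-test with a difference of 3.0 points, SD 3.8 and one-sided alpha 0.005. Exact noncentral-t power at N = 28 is 0.90991, as printed, and 28 / (1 − 0.30) = 40. The sizing reproduces and is not affected by this point. The 3.0 points serve below only as a yardstick. The second yardstick is the fall in the cited study, 15.3 − 4.7 = 10.6 points.

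**2. Largest shift per patient.** Maximum of 16A minus minimum of 16B = 2 − 0 = 2 points, provided code 3 is not summed. If it were, a 3 at V0 followed by 0 would give 3 points of false improvement, and a 3 at week 8 would count as worsening.

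**3. Mean shift.** Let p1 and p2 be the shares scoring 1 and 2 on 16A at V0 with weight already stable, so that 16B is 0 at both times. Mean artefact = 1 × p1 + 2 × p2. The documents give neither share. Assume p1 = 20% and p2 = 10% to 30%:

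- low: 0.20 × 1 + 0.10 × 2 = 0.4 points
- high: 0.20 × 1 + 0.30 × 2 = 0.8 points
- against 3.0 points: 0.4/3.0 = 13%, 0.8/3.0 = 27%
- against 10.6 points: 0.4/10.6 = 4%, 0.8/10.6 = 8%

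**4. Response.** With baseline b, of which h points come only from 16A, the plan counts response at a week-8 total of b/2 or less. With a consistent item the limit is (b − h)/2. The threshold therefore moves by h/2, at most 1 point. For example, with b = 16 and h = 2 the limit is 8 as planned and (16 − 2)/2 = 7 with a consistent item, so only a week-8 total of exactly 8 changes class.

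A simulation on whole-number scores used the cited means and SDs: V0 15.3 ± 3.8, restricted to the 8–24 entry range, and final score 4.7 ± 3.2. The correlation r between the two scores is an assumption, and h was assigned as in step 3.

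| r | Response as planned | h removed from V0, low | h removed from V0, high | Excess |
|---|---|---|---|---|
| 0 | 81.3% | 79.7% | 78.0% | 1.6 to 3.3 points |
| 0.5 | 87.4% | 85.7% | 83.9% | 1.7 to 3.5 points |

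**5. Remission.** This depends on the week-8 total alone, where a weight-stable patient scores 0 on item 16 under 16B and under any version confined to recent loss. At r = 0 it stays at 71.3%. Restricting to patients whose baseline would still be 8 or more moves it by at most 0.4 percentage points (r = 0.5).

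**The case against.** The best defence is that the switch belongs to the rating instructions reproduced in Appendix 1, that the study is descriptive, and that 0.4–0.8 points is small beside a fall near 10.6. The shares are assumed, and the calculation takes every affected patient as already stable at V0; someone still losing weight at V0 who then stops has truly improved. All of this stands. It limits the size of the point and argues against rewriting the item as the main remedy. It does not make the two ends of the change score comparable. The instructions do not forbid 16B at V0, but then sites may differ in their baseline version, which is no better.

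A reader might infer more than the documents support:

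- **False remission.** A patient entering at 8 with 2 points on 16A falls to 6 with nothing else changed, which looks like a spurious remission. Under a consistent recent-loss item that patient would score 6 at V0 and miss the 8–24 entry criterion. This is an eligibility effect. A larger remission effect appears only if the history points are added back at week 8, which no sensible correction would do.
- **A bias that always favours the drug.** A patient with no earlier loss (16A = 0) who loses more than 1 kg per week on therapy scores 2 on 16B, so the total rises.
- **16B cannot be rated.** Body weight is not listed for any visit, and the follow-up visits fall at weeks 2, 4 and 8, so the plan does not show how the rate is obtained. But a weekly rate can be derived from two weights some weeks apart or by asking the patient, and Table 1 does not itemise the inputs to any HAMD-17 item.
- **An inflated type I error.** With no true change and SD 3.8, a mean artefact of 0.4 points would raise rejection at a nominal 0.005 to about 0.02 at N = 28 and 0.043 at N = 70 (100 less 30% dropout). The hypothesis appears only in the sizing, and the planned analysis is descriptive, so this should not carry the argument.

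**Conclusion.** The point holds as a measurement inconsistency of modest size. Where 16A is used at V0, the primary change can contain up to 2 points per patient that reflect the change of version and not the patient. The mean artefact is 0.4–0.8 points, and the excess in response about 1.6–3.5 percentage points, if 20% score 1 and 10–30% score 2 on 16A and all of them are already weight-stable. Those shares are assumptions; fewer affected patients, or some still losing weight at V0, would give less. Remission is essentially unaffected, and individual patients can shift the other way. An effect as large as in the cited study would not be overturned. What is at risk is the accuracy of the reported change and response rate, which matters most for low baselines: 2 points is 25% of a baseline of 8 but 8.3% of a baseline of 24.

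**What to change.** Add to Biometrics a pre-specified sensitivity analysis that reports the primary change and the response rate on the HAMD-17 total without item 16 at both V0 and week 8. State in the same place that code 3 (not assessed) on item 16 is not summed into the total.

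Optionally, amend the Appendix 1 instructions so that one version of item 16, with one look-back period, is used at every visit. This is a larger step, because it alters the rating form.

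The sensitivity analysis uses data already collected and costs one table; sample size and visits do not change. Its drawbacks are that a 16-item total is less comparable with other studies and that it also removes any genuine change in weight loss. The gap between the two analyses therefore shows how much the result depends on item 16 and is not a pure estimate of the artefact.
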